6.1 General Study Design and Plan

[figure not shown]
Our primary hypotheses are that patients on dipyridamole will evidence a smaller increase in D-dimer levels and better clinical outcomes on the COVID ordinal score than patients on placebo.

This is a proof-of-concept, placebo-controlled, single-blinded, randomized, 14-day trial of 160 patients.

Participants were assigned treatments to dipyridamole or placebo in 1:1 fashion using stratified, random blocks based on sex and age (above/below 65). Stratified blocks were generated using the ‘blockrand’ package in R.

After randomization, treatment was administered four times daily up until hospital discharge or 14 days, with clinical evaluations made daily. Clinically significant abnormal lab studies were evaluated for relationship to the study drug. Clinical data capture and survival follow-up occurred on Day 28 \pm 1. Patient follow-up occurred again 30 days after last dose of study drug. The study schematic is presented in Figure 1.

Figure 1 Schematic Representation of Study Design

6.2 Inclusion-Exclusion Criteria and General Study Population

6.2.1 Inclusion Criteria

1. Age \geq 18 years
2. Willing and able to provide informed consent prior to performing study procedures unless they have a legally authorized representative (LAR)
3. Confirmed coronavirus (SARS-CoV-2) infection
4. Currently hospitalized or anticipated hospitalization requiring supplemental oxygen

6.2.2 Exclusion Criteria

1. In the opinion of at least two physicians, unlikely to survive for >48 hours from screening
2. Concurrent enrollment in a clinical trial of a cytokine inhibitor (targeting IL-6, IL-6R, IL-1, or Janus kinase). Use of remdesivir is permitted.

3. Currently on invasive mechanical ventilation
4. Hypotension defined as systolic blood pressure < 90 mmHg on two readings at least 4 hours apart
5. Pregnant or breastfeeding
6. Concurrent dual antithrombotic therapy (aspirin or P2Y12 inhibitor (eg. clopidogrel, ticagrelor) plus anticoagulation to treat deep venous thrombosis or pulmonary embolism (single antiplatelet agent, or anticoagulant agent at prophylaxis or therapeutic dose is permitted).
7. Presence of any of the following abnormal laboratory values: aspartate aminotransferase (AST) or alanine aminotransferase (ALT) greater than 5 x upper limit of normal (ULN), platelets <50,000 per mm³, hemoglobin <8 g per deciliter
8. History of recent major bleeding, defined in accordance with the criteria of the International Society on Thrombosis and Hemostasis (ISTH) as overt bleeding that was associated with a decrease in the hemoglobin level of 2 g per deciliter or more, led to a transfusion of 2 or more units of blood, occurred in a critical site within 30 days.
9. Any physical examination findings and/or history of any illness that, in the opinion of the study investigator, might confound the results of the study or pose an additional risk to the patient by their participation in the study.

6.3 Study Assessments

Table 1. Schedule of Events

Study Day	Screening Enrollment	Day 1	Days 3, 7, 11	Days 5, 9, 13	Even Days 2-12	Day 14	Day 28	Early Withdrawal	30 Days After Drug
Screening via chart review	X								
Screening for eligibility	X								
Informed consent	X								
Pregnancy test ^a	X								
Demographics		X							
Medical history		X							
Social history ^b		X							
Physical exam SOC review ^c		X							
Randomization	X								
Study drug administration		X	X	X	X	X			
Vitals/Oximetry SOC review ^c		X	X	X	X	X	X ^j	X	
Respiratory status SOC review ^c		X	X	X	X	X		X	
Clinical progress review		X	X	X	X	X		X	
Clinical care lab result review		X	X	X	X	X		X	
ECG clinical care data review ^d		X	X	X	X	X		X	
Chest imaging review ^d		X	X	X	X	X		X	
BMP ^e		X	X	X				X	
D-dimer ^e		X	X	X		X		X	
Ferritin ^e		X		X				X	
LDH ^e		X		X				X	
CRP ^e		X		X				X	
CBC w/ diff ^e		X	X	X		X		X	
FBN ^e		X	X	X		X		X	
PTT/INR ^e		X	X	X		X		X	
ABG ^d		X							
LFT ^e		X		X				X	
Research blood draw ⁱ		X ^f	X ^f	X ^f				X	
Concomitant meds/therapies		X	X	X	X	X	X ^g	X	
AE assessment		X	X	X	X	X	X ^g	X	X ^h

a Performed in subjects of child-bearing potential, if not already performed for clinical care reasons

b Social history including pregnancy history, tobacco and alcohol use

c Medical chart review for extraction of standard-of-care data.

d Only if performed while patient is inpatient/hospitalized for clinical care reasons. Data will be recorded.

e Lab results will be extracted from blood drawn for clinical care, whenever possible..

f Blood collection will be coordinated with blood draw for clinical care lab studies, whenever possible.

g Medical chart review for secondary endpoints will continue until Day 28.

h Chart review and phone call for AEs assessment until 30 days after last dose of study drug, maximum of 44 days from initial participation date.

i: Research lab draws on study days 3,5,9,11,13 will have +/- 1 day window.

Prior to conducting any study-related activities, written informed consent containing Health Insurance Portability and Accountability Act (HIPAA) authorization will be signed and dated by the participant.

6.4 Clinical Assessments

6.4.1 Concomitant medications

All concomitant medications will be documented during the study, including early termination when applicable. Dose, route, unit frequency of administration, indication for administration and dates of medication will be captured.

6.4.2 Demographics

Demographic information (race, ethnicity, sex, date of birth, and height and weight) will be recorded at the time of enrollment.

6.4.3 Medical history

Relevant medical history, including history of current disease and information regarding underlying diseases will be obtained from the patient and/or by chart review, and recorded at the time of enrollment.

6.4.4 Social history

Relevant social history, including history of pregnancy, tobacco and alcohol use, will be obtained from the patient and/or by chart review, and recorded at the time of enrollment.

6.4.5 Physical examination

A complete physical examination will be performed by the medical team during the hospitalization. Abnormal physical exam findings will be documented, and the principal investigator will incorporate this information into consideration of continued eligibility from a safety perspective.

6.4.6 Electrocardiogram

Electrocardiogram (ECG) will be performed by the medical team if clinically appropriate and documented in the eCRF if obtained.

6.4.7 Chest imaging

Chest imaging will be performed by the medical team if clinically appropriate and documented in the eCRF if obtained. Imaging findings will be coded in binary variables for infiltrates, pneumonia, pleural effusion, consolidation, pulmonary embolism, RV strain, and cardiomegaly.

6.4.8 Vital signs

Temperature, blood pressure, heart rate, respiration rate, height, weight will be performed per institutional protocol. Blood pressure will be measured at least twice daily.

6.4.9 Oxygen requirements

Pulse oximetry (SpO₂), oxygen requirements (mode of delivery), fraction of inspired oxygen (FiO₂), oxygen flow rate, and mode of mechanical ventilation will be recorded at least daily alongside vital signs measurement. Pulse oximetry will be measured at least twice daily.

6.4.10 Modified WHO COVID-19 8-point Ordinal scale assessment

Ordinal scale assessments will be made daily and on Day 28 as below:

Table 2. Modified COVID 8-Point Ordinal Scale

Patient State	Descriptor	COVID Ordinal Score
Dead	Death	8
Hospitalized – severe disease	Ventilation + additional organ support (pressors, renal replacement therapy, ECMO)	7
	Intubation and mechanical ventilation	6
	Non-invasive ventilation or high-flow oxygen	5
Hospitalized – mild disease	Oxygen by mask or nasal prongs	4
	Hospitalized, no oxygen therapy	3
Ambulatory	Limitation of activities	2
	No limitation of activities	1

6.4.11 National Early Warning Scores (NEWS2)

The NEWS2 score will be made daily and on Day 28. We omit details of NEWS2, because it will not be analyzed in this SAP.

6.4.12 Adverse events

Information regarding occurrence of adverse events will be captured throughout the study. Duration (start and stop dates), severity/grade, outcome, treatment and relation to study drug will be recorded on the source document.

6.5 Clinical Laboratory Measurements**6.5.1 D-dimer, Ferritin, lactate dehydrogenase (LDH), C-reactive protein (CRP), complete blood cell count with differential (CBC), fibrinogen, partial thromboplastin time (PTT), international normalized ratio (INR), arterial blood gases (ABG), basic metabolic panel (BMP), hepatic function panel (LFT)**

We anticipate blood will be drawn for clinical care at least every other day, and anticipate that most research blood studies will be performed on blood already drawn for clinical care. We will also extract data for any studies done for clinical care purposes. Blood will be obtained and sent to the clinical laboratory to measure LDH, CBC, CRP, D-dimer for standard of care at the discretion of the medical team. D-dimer, fibrinogen, PTT, INR, ferritin, CBC, LFT, LDH, CRP, BMP will be measured on day 1 on blood drawn for clinical care. Although daily measurement of D-dimer would be ideal for the primary endpoint of this research study, we will measure D-dimer every other day given ongoing medical resource constraints. D-dimer, fibrinogen, PTT, INR and CBC will be measured on days 3, 5, 7, 9, 11, 13 and 14 during hospitalization. CRP, ferritin, LDH, BMP will be measured on day 1, 5, 9, and 13, during hospitalization for research study using blood drawn for clinical care wherever possible. LFT will be measured on day 1 for clinical care, and at least every 4 days until end of drug treatment phase in blood drawn for clinical care wherever possible during hospitalization. ABG will only be recorded if performed for clinical care purposes.

6.5.2 Pregnancy test

A urine pregnancy test, if not already performed for clinical care, will be obtained from female patients who are of childbearing age by the medical team prior to obtaining informed consent.

6.5.3 Pharmacokinetic measurements

Not applicable.

6.6 Research Laboratory Measurements (see Schedule of Events)

6.6.1 Coagulation potential

Blood will be obtained to investigate potential mediators of COVID-19 and novel parameters of coagulation and platelet activity measured in the study team's research laboratories.

6.6.2 Biomarkers of blood cell activation

Blood will be collected in sodium citrate, heparin, EDTA or serum separator tubes. The blood sample will be labelled and processed at the local sites before shipping to the study team's research laboratories at the University of Michigan to evaluate novel biomarkers of blood cell activation, coagulation, and cytokines.

6.6.3 Leukocytes

Blood will be collected in EDTA, sodium citrate, or heparin tubes. The blood sample will be labelled and sent for processing to the clinical and research labs.

7 Sample Size

7.1 D-dimer Calculations

Decision thresholds and power calculations are based on a preliminary analysis of 147 D-dimer measurements taken on 41 COVID-19 patients in the University of Michigan hospital in Spring 2020. Quantities were estimated through simulation based on the preliminary data.

The presumed analysis is a variance components regression on log-transformed D-dimer values with fixed effects for ICU status (a binary proxy for case severity) and days since admission. The model assumes random effects for linear subject-level log-D-dimer trends over time. We set an intraclass correlation coefficient (ICC) of 0.7, which reflects large between-subject variation relative to within-subject variation and is conservatively lower than the observed ICC of 0.77.

Power is based on a mean 13% daily increase in D-dimer levels for untreated patients, as observed in preliminary analysis. We posited a 50% reduction in the growth rate (i.e. 6.5% daily increase) for the 100 mg dose of study drug. Based on 2 arms with 40 subjects per arm (80 subjects in all), power is 0.91 for comparing the pooled dipyridamole participants to the controls.

7.2 Win Ratio Calculations

The standard of care treatment for COVID-19 changed with the introduction of anti-inflammatory steroids, which appear to influence D-dimer concentrations. It was therefore determined to elevate the secondary endpoint to become a co-primary endpoint. This endpoint is a composite of clinical outcomes including death, survival time, mechanical ventilation days, decrease in SpO₂/FiO₂ ratio, and cumulative COVID-19 ordinal scores.

This endpoint will be assessed nonparametrically by comparing outcomes across all possible pairs of treatment-placebo patients and evaluating a 'win ratio' using the Mann-Whitney U-statistic (Pocock et al., 2012). See Section 8.6.2.2 for details. The win proportion is interpreted as the probability that a study drug patient experiences a better outcome than a placebo patient, and in this sense, it represents the effect size for the analysis. We powered our analysis on a presumed 0.67 win proportion (i.e. a patient on study drug is twice as likely to have a better outcome as a patient on placebo). We calculated sample size requirements using the formulas provided in Yosef et al. (2019).

Because we set a 0.006 Type I error significance (alpha) for the interim analysis for benefit of D-dimer, we could only use 0.044 of the original 0.05 for the primary endpoints. We divided the 0.044 between the two co-primary endpoints, leaving a 0.022 two-sided Type I error. Accounting for a 10% dropout, we require 127 patients to have 80% power to significantly detect a win ratio of 0.67.

8 General Analysis Considerations

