The win proportion is the probability that a treatment patient experiences better outcomes when compared to a placebo patient, thus representing the effect size. The analysis is powered to a 0.67 win proportion. For the efficacy endpoint using the O'Brien-Fleming method to correct for interim analyses, we will use a P value cutoff of 0.006 for the midway point analysis and 0.044 for the final analysis, yielding an overall alpha (type I error rate) of 0.05.

15.3.1 *Interim Analyses of Primary Endpoints*

When approximately 25% and 50% of participants have completed the study or 10 deaths have occurred (whichever occurs first), an interim analysis for safety and futility will be conducted by the DSMB. The interim analyses for efficacy will be limited to the review after 50% of participants have completed the study to limit the cost to power from multiple interim analyses.

The interim analysis of benefit for the primary endpoint will be conducted on a binary version of patient-level D-dimer change rates. Rates will be estimated separately for each patient by simple linear regression and dichotomized by whether the rates was above a 5% daily increase.

Treatment groups will be compared by a Fisher's exact test. We will use the O'Brien-Fleming method and Lan-DeMets alpha spending functions to preserve an overall Type I error rate of 0.05. Thus, the interim analysis will use a significance threshold of $\alpha = 0.006$ (based on 45 patients), and the remaining 0.044 of alpha will be divided evenly between the final analyses of the two primary endpoints.

For futility of the D-dimer endpoint, if the lower limit for the 95% confidence interval of the daily change in D-dimer is above 9% *for the dipyridamole population* at the time of the 50% interim analysis, the trial will be stopped.

It was decided in the December 2020 DSMB meeting to conduct benefit and futility analyses of the composite hierarchical primary endpoint for all patients with study completion as of December 31, 2020. We proceed with the win ratio analysis described above but base futility and benefit decisions on the conditional power approach described in Lan and Trost (1999) and advanced in Siu and Lan (2001) and Lachin (2006). This approach calculates the condition power (CP), defined as the probability of finding a significant result at the end of the study given the interim results and a presumption that the data reflect the true effect size. Decision thresholds are predetermined as:

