8.7 Multiple Testing

In the primary analyses, we use the O’Brien-Fleming method to correct for interim analyses and the Lan-DeMets spending function to preserve an overall Type I error rate of 0.05. We will use a Bonferroni adjustment to maintain familywise error for the five secondary analyses. We will not apply a multiple testing adjustment to exploratory endpoints; any findings associated with exploratory endpoints will require confirmation before reporting.

9 Summary of Study Data

Descriptive summary statistics will be tabulated for baseline patient demographics and clinical characteristics separately by intervention group and overall. All tables will be annotated with the total population size relevant to that table (usually the mITT), including missing observations. For continuous variables, the estimated mean, standard deviation, median, minimum, and maximum will be reported. For categorical variables, number and percentages will be reported (excluding missing values).

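### The fixed 0.022/0.022 split for the primaries and Bonferroni for the five secondaries are valid, but Holm's step-down gives at least as much power at the same familywise level

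*SAP*

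**What the plan says.** SAP 7.2 first sets aside the interim spend: "Because we set a 0.006 Type I error significance (alpha) for the interim analysis for benefit of D-dimer". It then says: "We divided the 0.044 between the two co-primary endpoints, leaving a 0.022 two-sided Type I error". SAP 10.1 and 10.2 repeat 0.022 for each primary analysis. Protocol 15.3.1 agrees that "the remaining 0.044 of alpha will be divided evenly between the final analyses of the two primary endpoints".

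For the secondary endpoints, SAP 8.7 states: "We will use a Bonferroni adjustment to maintain familywise error for the five secondary analyses". The five are listed in SAP 10.3: the four components of the composite, plus days alive and free of organ support. The level of that family is not given.

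Neither document lets alpha pass from a rejected hypothesis to one still open, and neither names a step-down or gatekeeping procedure. Neither says in words whether the trial succeeds on one primary endpoint or needs both. The endpoints are called co-primary, but dividing alpha between them only makes sense if either one suffices.

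**The concern.** Under a fixed split, each primary endpoint stays at 0.022 even after the other has been rejected. The five secondary tests are likewise each held at one fifth of their family level, whatever the others show. Holm's procedure relaxes the later thresholds after each rejection, keeps strong familywise control, and needs no assumption about how the tests are correlated. That last property matters here because four of the five secondaries are parts of one composite.

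What is at stake is power. According to the Protocol synopsis, enrolment was halted at 100, against the 127 that SAP 7.2 requires for 80% power on the composite. Protocol 15.3 explains that the composite was promoted because changes in standard care had reduced the value of D-dimer. A rule that could recover part of the lost power on the composite, at no cost in alpha, deserves consideration.

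**Working it through.** **Inputs.** Interim spend 0.006 and final level 0.022 per primary (SAP 7.2). Composite effect: "We powered our analysis on a presumed 0.67 win proportion". Sample size: "Accounting for a 10% dropout, we require 127 patients to have 80% power to significantly detect a win ratio of 0.67". Allocation 1:1 (SAP 6.1). D-dimer: "Based on 2 arms with 40 subjects per arm (80 subjects in all), power is 0.91" (SAP 7.1). Enrolment 100 (Protocol synopsis). Assumed, because the documents do not say: the 0.91 refers to a two-sided 0.05 test; the secondary family level is 0.05; all 100 patients are evaluable.

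**1. Reproduce the plan's N.** Noether's formula for the Mann-Whitney test with equal arms is N = (z(1-α/2) + z(power))² / (3(p - 0.5)²). With α = 0.022, power 0.80 and p = 0.67: (2.290 + 0.842)² / (3 × 0.17²) = 113.1, rounded up to 114. Then 114 / 0.9 = 126.7, rounded up to 127. This matches the SAP, so the same formula can be used for power.

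**2. Alpha accounting.** The plan spends 0.006 + 0.022 + 0.022 = 0.05. Under Holm:
- If both final nulls are true, a false rejection needs the smaller p-value to be at or below 0.022. That is the same event as under the fixed split, with probability at most 0.044 (simulated 0.0437 at correlation 0 and 0.0412 at 0.5).
- If only one null is true, it is rejected only if its p-value is at or below 0.044.
- With the interim spend, the total is at most 0.006 + 0.044 = 0.05.

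**3. Power for each primary at N = 100.**
- Composite: Φ(√(3 × 100) × 0.17 - z), which is 0.743 at 0.022 and 0.824 at 0.044.
- D-dimer: the shift behind 0.91 at 0.05 is 1.960 + 1.341 = 3.301. Power is therefore Φ(3.301 - 2.290) = 0.844 at 0.022 and Φ(3.301 - 2.014) = 0.901 at 0.044.

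**4. Holm against the fixed split, tests taken as independent.**
- Composite under Holm: 0.743 + 0.844 × (0.824 - 0.743) = 0.811.
- Winning both, fixed split: 0.743 × 0.844 = 0.627.
- Winning both, Holm: 0.844 × 0.824 + 0.901 × 0.743 - 0.627 = 0.738.
- At least one win, either procedure: 1 - (1 - 0.743)(1 - 0.844) = 0.96.

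**5. Sensitivity of the composite gain.**

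| Setting | Fixed split | Holm |
|---|---|---|
| N = 100, D-dimer power 0.91 at 0.05 | 0.743 | 0.811 |
| N = 100, D-dimer effect as planned, its power scaled from 80 to 100, correlation 0 to 0.6 | 0.744 | 0.814-0.817 |
| N = 114 evaluable, as planned, correlation 0 to 0.6 | 0.803 | 0.864-0.867 |
| N = 100, half the planned D-dimer effect, correlation 0 to 0.6 | 0.744 | 0.754-0.770 |
| N = 100, no D-dimer effect | 0.743 | about 0.744 |

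In the last row, the gain can be at most 0.022 × (0.824 - 0.743) = 0.002 if the tests are independent.

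**6. Secondaries.** The Holm thresholds are 0.05/5, 0.05/4, 0.05/3, 0.05/2 and 0.05, that is 0.01, 0.0125, 0.0167, 0.025 and 0.05, in place of 0.01 throughout. The simulation gave each true effect 80% power at 0.05 and used correlations of 0 and 0.5. Average power for the true effects:

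| True effects | Bonferroni | Holm |
|---|---|---|
| 1 | 0.59 | 0.59 |
| 3 | 0.59 | 0.62-0.63 |
| 5 | 0.59 | 0.69-0.70 |

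Simulated familywise error under Holm did not exceed 0.046.

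**The case against.** The strongest reply is that nothing is broken. The split is valid, prespecified and stated the same way in SAP 7.2, 10.1 and 10.2 and in Protocol 15.3.1, and 127 is correctly sized at 0.022. This stands: a reader might infer from the lost power that the error control is wrong, and it is not.

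The second reply is that the headline gain rests on effects that the documents themselves now doubt. Holm helps only after a first rejection. Protocol 15.3 questions whether D-dimer is still clinically meaningful, the 0.91 comes from patients of spring 2020, and recruitment was halted for futility, without a statement of which endpoint drove the halt. This also stands: the realised gain may be close to zero. The planned 10% dropout lowers the starting point as well: with 90 evaluable patients, composite power at 0.022 is 0.69, not 0.74.

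Third, the change is not wholly free. A fixed 0.022 test pairs with a plain 97.8% interval, while Holm has no equally simple counterpart. A rule relaxed after the interim looks also has to be documented openly. Both points stand, but they are small. The step-down reaches the same first rejection as before, and SAP 8.1 starts the final analysis only after the SAP is approved.

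A reader might also infer that Holm is the only way to recover this power. It is not: unequal weights or a fallback sequence could also raise power for one endpoint.

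**Conclusion.** The point holds as an optional, low-cost gain in efficiency. At N = 100 with a win proportion of 0.67 and D-dimer power of 0.91 (taken at two-sided 0.05), Holm adds about 7 points to composite power (0.74 to 0.81) and about 11 points to the chance of winning on both (0.63 to 0.74). If D-dimer has no effect, the composite gain is about zero. In every case the chance of at least one win, and the N of 127, stay where they are. The size of the secondary gain depends on how many of the five effects are real; the figure for five is a best case.

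Two stronger readings lack support. The label co-primary might suggest that both endpoints must succeed, but no passage says so and the alpha split implies the opposite. Holm might also be taken to put the plan's alpha in order. It does not. These conflicts remain and need separate reconciliation: the interim level of 0.003 (SAP 8.6.2.1) against 0.006 (SAP 10.1 and 10.2); the final levels of 0.044 (Protocol 15.3) and 5% (SAP 10) beside 0.022; and the stop for benefit at conditional power of 0.9 or more without an alpha adjustment (Protocol 15.3.1, SAP 8.6.2.2). The bound of 0.05 shown above takes 0.006 as the only earlier spend.

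**What to change.** Write the following into SAP 8.7, 10.1 and 10.2 and Protocol 15.3.1, as a dated change made before the final unblinded analysis:

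- Success may be claimed on either primary endpoint. The smaller of the two final p-values is tested at 0.022; if it is significant, the other is tested at 0.044.
- The five secondary analyses are tested by Holm's procedure in place of Bonferroni, at a stated family level.
- 97.8% intervals for the primaries are still reported, with a note that they may not match the step-down decision for the second endpoint tested.

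The cost is a few sentences. Alpha and sample size are unaffected, and 127 remains the figure for sizing the composite at 0.022.
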